3.1 Discussion of Study Design

This is a Phase 2, multi-centre, open-label, prospective, 2-period, bilateral interventional safety study of timrepigene emparvovec in adult male subjects with genetically confirmed CHM.

The study will consist of a Screening Period followed by 2 treatment periods (Period 1 and Period 2) with up to 9 visits per treatment period. A second baseline visit prior to surgery of Study Eye 2 (SE2) (Period 2, Visit 1) may be required. A study schematic is presented in [Figure 1](#).

Figure 1 Overall Study Schematic

During the Screening Period, subjects will be assessed for eligibility of both eyes. The investigator will assign the order in which the eyes are treated (i.e., study eye 1 [SE1] period 1 and study eye 2 [SE2] period 2, respectively) with a number assigned to each eye. This will be done in collaboration with the subject; however, the worse eye will generally be selected for first treatment. The estimated target interval between the surgical procedures of SE1 and SE2 will be determined at the Screening Visit.

Each study eye will be followed for at least 12 months post-treatment, for up to 9 visits per treatment period: Visit 1 (Day 0, Injection Day Visit); Visit 2 (Day 1, post-operative follow up visit); Visit 3 (Day 3 + 2 Days); Visit 4 (Day 7 -1/+2 Days); Visit 5 (Day 14 ± 3 Days); Visit 6 (Month 1 ± 7 Days); Visit 7 (Month 3 ± 14 Days); Visit 8 (Month 6 ± 14 Days) and Visit 9 (Month 12 ± 14 Days).

The interval between SE1 and SE2 treatment is expected to vary among subjects from weeks to many months. While the interval will be decided on a case-by-case basis, an effort will be made to schedule varying treatment intervals in order to better characterise the immunological and safety profile of sequential treatment administration. Thus, approximately 20 subjects each will be treated with a short- (<6 month), medium- (6-12 months), or long- (>12 month) surgery window between treatment of the first and second eye. Because the timing of the second surgery visit (Period 2, Visit 1) will vary among subjects, the duration of study Period 1 will also be variable.

All baseline ophthalmic assessments must be conducted within 3 months prior to SE2 surgery (Period 2, Visit 1). If these assessments are not available within the required timeframe, a Baseline Visit must be added to collect current baseline data on SE2. If, at that time, BCVA in SE2 is <34 ETDRS letters, surgery may be performed when, in the opinion of the

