3.3 Study Schedule

At Period 1, Visit 1 (Day 0, Injection Day Visit for SE1), subjects will undergo a vitrectomy with retinal detachment and receive a sub-retinal injection of timrepigene emparvovec in SE1. Visits 2-9 will then be conducted according to the Schedule of Study Procedures, unless Period 2 commences during the time of follow-up for SE1; in which case, the study visits will continue following the schedule for SE2. Ophthalmic assessments during Period 1, Visits 2-9 will be performed on both eyes.

At Period 2, Visit 1 (Day 0, Injection Day Visit for SE2), subjects will undergo a vitrectomy with retinal detachment and sub-retinal injection of timrepigene emparvovec in the contralateral, untreated eye (SE2). Post-treatment, subjects will no longer follow the Period 1 visit schedule, but will instead attend Period 2, Visits 2-9 according to the Schedule of Study Procedures. Ophthalmic assessments scheduled for Period 2, Visits 2-9 will be performed on both eyes.

Study data will thus be collected for both eyes in each subject. Subjects will be assessed for safety and efficacy throughout the study, as outlined in the Schedule of Study Procedures ([Section 7.2](#)).

A subject is considered to have completed the study if he completes Period 2, Visit 9 (Month 12). The end of the trial is the date the last subject completes Period 2, Visit 9 (Month 12) assessments (or early termination [ET] assessments in the event of premature discontinuation) or the date of last data collection if the last subject is lost to follow-up.

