3.6 Sample Size

Approximately 60 subjects are planned to be enrolled in the study. A total of 120 treated eyes is considered sufficient to characterise the immunological profile of bilateral timrepigene emparovovec administration, which is the key concern of gene therapy re-administration.

4 Statistical Methodology

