4.3 Definitions

Study Eye 1 (SE1) is defined as the first treated eye (within GEMINI or in an antecedent clinical trial). **Study Eye 2 (SE2)** is defined as the second treated eye (irrespective of whether the first eye was treated in GEMINI or in an antecedent clinical trial). Subjects whose first eye is treated in an antecedent study will contribute to Period 2 only (except for the immunogenicity analyses), where Study Eye 1 is the eye treated in the antecedent study and Study Eye 2 is the eye treated in GEMINI.

Period 1 starts on the day of the surgery of the first treated eye and ends on the day prior to the day of the surgery of the second treated eye. **Period 2** starts on the day of the surgery of the second treated eye.

Baseline Value of Period 1/2 is defined as the last non-missing value prior to treatment of the respective period. Baseline of each period for each eye will be used to calculate the change from baseline for the data in the same period and same eye. For example, period 1 SE1 baseline will be used to calculate the change from baseline for all the data of SE1 in period 1, whereas period 2 SE1 baseline will be used to calculate the change from baseline for all the data of SE1 in period 2.

For immunogenicity, baseline will be defined separately in [Section 4.17.11](#).

Analysis day for all the post-baseline visits will be calculated as the date of the post-baseline visits minus the corresponding injection date, depending on which baseline that was used.

For the 6 subjects whose first eye was treated in the antecedent study (Subjects [REDACTED], [REDACTED], [REDACTED]), only period 2 data are collected in GEMINI. Therefore, only period 2 data will be presented for these 6 patients.

Change from Baseline is defined as the difference of the value of an assessment at the considered visit from the baseline value of the corresponding period.

Duration is measured in days and is calculated as end date – onset date + 1.

Injection dates of SE1 and SE2 will be coded **Day 0** for the Period 1 and Period 2 respectively.

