4.8 Handling of Missing Values

The number, pattern and timing of missing data will be examined along with the reasons for withdrawal or for missing data.

The safety analyses will be performed using the ‘observed case’ method. In the efficacy analysis, observed case method will be applied as main analysis for categorical and continuous endpoints. The following supportive analysis will be performed for BCVA related endpoints: both categorical endpoints and continuous endpoints will be imputed using the ‘Last Observation Carried Forward’ (LOCF) method with the last available measurement prior to missing (see details in [Section 4.16.1](#)).

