4.16.1 Visual Acuity

Best-corrected visual acuity (BCVA) and change from baseline will be summarised by visit, by eye, by period as well as overall. The corresponding 95% CIs will be calculated (See [Section 4.2](#)).

Furthermore, the proportion of eyes with a ≥ 10 letters increase, a ≥ 15 letters increase, and an increase or a loss < 5 letters (i.e. change from baseline > -5 letters) will be summarised by visit, by eye, by period as well as overall. The corresponding 95% CI will be presented (See [Section 4.2](#)).

The above main analyses will use the observed case method only. Imputation using LOCF method regardless of the reasons of missing data will be performed for supportive analyses (See [Section 4.8](#)).

In addition to the by-period, by-eye presentation mentioned above, as supportive analyses, for both continuous and categorical endpoints, the period 2 Study Eye 1 data will be presented by

remapping them to visits after their last visit in period 1 and calculating change from baseline using baseline at period 1 for the same eye (Study Eye 1). This way a full picture of Study Eye 1 treatment journey during the entire study will be presented.

For all assessments of periods 1 and 2 of Study Eye 1, the data records will be assigned to calculated visit window (using study day) as described in [Table 2](#) below. The window of the visits following baseline (including unscheduled visits) will be constructed in such a way that the upper limit of the interval falls half way between the two visits.

If a patient has more than one assessment included within a window, the assessment closest to the target day will be used. In case of ties between observations located on different sides of the target date, the value with the later date will be used.

Table 2 **Visit Assignment Windows**

Day / Month	Target Day	Day Range included in the visit
Baseline	0	The last assessment on or before day 0
Day 1	1	Day 1
Day 3	3	Day 2 to 5
Day 7	7	Day 6 to 10
Day 14	14	Day 11 to 22
Month 1	30	Day 23 to 61
Month 3	91	Day 62 to 136
Month 6	182	Day 137 to 272
Month 9	273	Day 228 to 318
Month 12	365	Day 319 to 410
Month 15	456	Day 411 to 501
Month 18	548	Day 502 to 593
Month 21	639	Day 594 to 684
Month 24	731	Day 685 onwards

Both continuous and categorical endpoints for BCVA will be summarised by subgroups mentioned in [Section 4.7](#).

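### The supportive LOCF rule for BCVA does not exempt Period 1 visits that second-eye surgery cancels by design; read literally, it would fill roughly 54–74% of Study Eye 1 Month 12 values in Period 1

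*SAP*

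**What the plan says.** SAP 4.16.1 summarises BCVA by visit, eye and period. The main method is clear: "The above main analyses will use the observed case method only". A supportive version follows: "Imputation using LOCF method regardless of the reasons of missing data will be performed for supportive analyses". SAP 4.8 says what is carried, namely LOCF "method with the last available measurement prior to missing".

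Period 1 has a variable length. Under SAP 4.3 it "ends on the day prior to the day of the surgery of the second treated eye". SAP 3.3 says what happens to the visits: "Post-treatment, subjects will no longer follow the Period 1 visit schedule, but will instead attend Period 2, Visits 2-9". Protocol 7.1 says the same.

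The spacing of the two operations is planned in SAP 3.1: "Thus, approximately 20 subjects each will be treated with a short- (<6 month), medium- (6-12 months), or long- (>12 month) surgery window". SAP 4.3 adds that six subjects had their first eye treated in an antecedent study and contribute Period 2 data only.

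SAP 4.16.1 also plans a separate supportive presentation for SE1. It places the Period 2 measurements of that eye on its own time axis and measures change from the Period 1 baseline.

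**The concern.** A Period 1 visit that falls after SE2 surgery was never due. It is a feature of the design, not a lost observation. The LOCF rule applies whatever the reason for the gap, and nothing in 4.8 or 4.16.1 separates a visit that was missed from one that was not scheduled.

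Taken at its word, the rule gives every short-window subject a Month 6 and a Month 12 value for SE1 in Period 1, and gives most medium-window subjects a Month 12 value. None of these was measured at that time. Meanwhile the same eye continues to be measured in Period 2.

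At stake are the supportive mean change and the 10- and 15-letter gain proportions for SE1 at those visits. They would mix observed values with values from other times, and the t and Clopper-Pearson intervals would use an n that looks nearly complete. The remapped SE1 presentation could then show a different value for the same eye at the same nominal visit.

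**Working it through.** **Inputs**

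- Planned enrolment of about 60 (SAP 3.6) and about 20 subjects per window (SAP 3.1). Check: 3 × 20 = 60, so the two agree.
- Six subjects without Period 1 data (SAP 4.3). Assuming they are among the 60, SE1 eyes with a Period 1 number 60 − 6 = 54.
- Month 12 visit ± 14 days, opening at about Day 365 − 14 = 351. SAP Table 2 assigns Days 319–410 to Month 12.

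The documents give neither a share of imputed values nor actual window sizes, so there is no stated figure to reproduce beyond the total of 60.

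**Month 12: share filled by design = (short + medium eyes with a Period 1) / 54**

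| Where the six antecedent subjects fall | Filled | Share |
|---|---|---|
| all long window | 40/54 | 74% |
| spread evenly, so four are short or medium | 36/54 | 67% |
| all short or medium | 34/54 | 63% |

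Some medium-window subjects may have a Month 12 value before surgery. As an assumption, spread medium-window surgery evenly over Days 182–365, which is 183 days.

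- Protocol visit window: 20 × (365 − 351)/183 = 1.5 subjects. With all six antecedent subjects long-window, (40 − 1.53)/54 = 71%.
- Table 2 window: at most 20 × (365 − 319)/183 = 5.0 subjects. This gives (40 − 5.03)/54 = 65%, or (34 − 5.03)/54 = 54% if all six antecedent subjects are also short or medium.
- If half the medium group had an observed Month 12 value first and all six antecedent subjects were long-window: (40 − 10)/54 = 56%.

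Subjects never treated in SE2 stay on the Period 1 schedule (Protocol 8.3) and lower the share. Three such subjects from the short or medium groups give 37/54 = 69%, and six give 34/54 = 63%. Dropout in the long window would raise it. In addition, Protocol Table 1 schedules no BCVA on the injection day, so surgery timed to coincide with Month 12 yields a Period 1 Month 12 value only if BCVA was measured before that day.

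**Month 6: the short window alone**

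None of the six antecedent subjects short-window: 20/54 = 37%. Two of the six short-window: 18/54 = 33%.

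**What is carried**

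- Short window: anything from an early post-operative value up to one taken close to Month 6. Protocol 9.8 provides for SE2 surgery before Study Day 21, so a Day 14 value is possible. The documents do not say how often.
- Medium window: normally the Month 6 value, or the Period 2 baseline BCVA. Protocol 7.1 and 10.1.1 require that baseline within 10 weeks before SE2 surgery, so it usually falls inside Period 1.

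**Effect on the interval**

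The SAP's half-width is t(0.975, n − 1) × SD/√n. At equal SD:

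- n = 54: 0.273 SD
- n = 18, long-window eyes if the six are spread evenly: 0.497 SD
- n = 14, long-window eyes if all six are long-window: 0.577 SD

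The filled table's interval is therefore 1 − 0.273/0.497 = 45% to 1 − 0.273/0.577 = 53% narrower than the one the long-window eyes alone support. The added values hold no Month 12 measurement.

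**The case against.** **Whether the rule applies at all.** SAP 4.3 closes Period 1 the day before SE2 surgery, and SAP 3.1 speaks of up to nine visits per period. On those definitions a later Period 1 visit does not exist for that subject and need not count as missing. This is a fair alternative reading. The SAP never states it, however, and a rule that disregards the reason for the gap points the other way. That leaves the handling to the programmer.

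**How early the carried values are.** A reader might infer that SE1 results at Months 6 and 12 would mostly reflect early post-operative vision. The documents do not support that. At Month 6 only about a third of values are filled. At Month 12 the medium-window carried values come from around Month 6 or later, so only the short-window share (33–37%) could be early, and many of those may be Month 3 values or later.

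**Whether two thirds is a floor.** It is not. Window sizes are only planned, the placement of the six antecedent subjects is not given, and late medium-window surgery or an untreated second eye lowers the share.

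**How much it matters.** The main efficacy analysis uses observed cases, as do the BCVA-loss proportions in SAP 4.17.1. No formal comparison is made. The remapped SE1 series already reports the later data, BCVA is also summarised by surgery window, and SAP 4.10 tabulates attendance. All of this stands and limits the damage to the supportive LOCF tables. It does not make those tables right.

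**Conclusion.** The gap in the rule is real. Read literally, it would fill roughly 54–74% of SE1 Month 12 values and about one third of SE1 Month 6 values in the Period 1 LOCF tables with measurements from other times, and would give intervals that are too narrow.

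The range rests on about 20 subjects per window, on the six antecedent subjects being among the roughly 60, and on an even spread of medium-window surgery for the lower end. It describes the cases worked through and is not a hard bound. Actual surgery dates will settle the figure.

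The direction of any bias cannot be told from the documents. Early values may catch transient post-operative loss, and they may also miss later change such as cataract.

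A reader might take this as a threat to the study's safety conclusions. It is not, because only supportive LOCF output is touched. It should still be corrected, since the protocol (13.2) named LOCF as the efficacy imputation and readers will look for this table.

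**What to change.** Add to SAP 4.8 and 4.16.1 that, in the by-period tables, LOCF applies only to visits due before that subject's SE2 surgery, and that later Period 1 visits are shown as not applicable. For SE1 at Month 6 and Month 12, refer the reader to the remapped SE1 series, with LOCF there only for visits truly missed.

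Two details need settling in that series:

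- Table 2 gives Month 6 as Days 137–272 and Month 9 as Days 228–318, which overlap. The SAP's own half-way rule, (182 + 273)/2 = 227.5, would end Month 6 at Day 227.
- The remapped series does not give every short-window eye a Month 12 value. With SE2 surgery on Day S after SE1 treatment and visits on target, the Period 2 Month 6 visit falls on Day S + 182 and the Month 12 visit on Day S + 365. Surgery between Day 46 and Day 136 puts these at Days 228–318 and 411–501, both outside Days 319–410. Such cells should be shown as not scheduled and left unfilled.

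The cost is a short addition to the SAP, one programming condition, and a smaller n in the supportive by-period table. At Month 12 that table would rest on the long-window subjects (14 to 18 of 54 in the two main cases), plus any medium-window subjects measured before surgery and any never treated in SE2. No new data are needed.

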The interval between SE1 and SE2 treatment is expected to vary among subjects from weeks to many months. While the interval will be decided on a case-by-case basis, an effort will be made to schedule varying treatment intervals in order to better characterise the immunological and safety profile of sequential treatment administration. Thus, approximately 20 subjects each will be treated with a short- (<6 month), medium- (6-12 months), or long- (>12 month) surgery window between treatment of the first and second

eye. Because the timing of the second surgery visit (Period 2, Visit 1) will vary among subjects, the duration of study Period 1 will also be variable.

The post-operative outcome and visual function of SE1 will inform the scheduling of Period 2. Signs of post-operative inflammation or other post-operative sequelae, as judged by the Investigator, should be resolved in SE1 for the subject to continue to Period 2. After comprehensive evaluation of all safety assessments and visual functional tests of SE1 and SE2, the Investigator will determine the eligibility of the subject and decide the appropriate time to schedule SE2, Visit 1.

All baseline ophthalmic assessments must be conducted within 10 weeks prior to SE2 surgery (Period 2, Visit 1). If these assessments are not available within the required timeframe, a Baseline Visit must be added to collect current baseline data on SE2. Study eye selection and eligibility for surgery will then be confirmed collectively by the Patient Eligibility Review Committee, which includes the Investigator, a consulting surgeon, and the Sponsor (see the Patient Eligibility Review Plan). If, at that time, BCVA in SE2 is <34 ETDRS letters, surgery may be performed when, in the opinion of the Patient Eligibility Review Committee: 1) the subject is found eligible by all other inclusion and exclusion criteria, and 2) the subject is considered an appropriate candidate who has potentially modifiable disease.

At Period 2, Visit 1 (Day 0, Injection Day Visit for SE2) subjects will undergo a vitrectomy with retinal detachment and sub-retinal injection of AAV2-REP1 in the contralateral, untreated eye (SE2). Post-treatment, subjects will no longer follow the Period 1 visit schedule, but will instead attend Period 2, Visits 2-9 according to the Schedule of Study Procedures. Ophthalmic assessments scheduled for Period 2, Visits 2-9 will be performed on both eyes.

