7.2 Discussion of Design

Since CHM is a bilateral disease, this open-label study is being conducted to assess the safety of AAV2-REP1 administered to both eyes of subjects with CHM. All enrolled subjects will receive treatment with AAV2-REP1 at a dose of 1×10^{11} AAV2-REP1 gp/eye. Bilateral sub-retinal administration of AAV2-REP1 was explored in a pre-clinical toxicology study in rats and was found to be well tolerated and not associated with drug-related AEs. Furthermore, sequential sub-retinal administration of an AAV2 vector to the contralateral eye in children and adults with Leber's congenital amaurosis was demonstrated to be safe and efficacious, irrespective of baseline immune status ([Bennett, Wellman et al. 2016](#)).

The planned sample size (approximately 60 subjects, with a total of 120 treated eyes) is considered sufficient to characterise the immunological, vector shedding, and safety profiles of bilateral retinal gene therapy with AAV2-REP1. A prospective trial period of at least 12 months following the administration of AAV2-REP1 in each eye is considered a sufficient period of time to observe any treatment related safety concerns.

The dose of vector being employed in this study is based on previous clinical trials using the AAV2 vector with a chicken β actin (CBA) promoter ([Maguire, High et al. 2009](#), [MacLaren, Groppe et al. 2014](#)), and the Phase 1 / 2 investigator-sponsored clinical studies in which AAV2-REP1 was administered to subjects with CHM ([MacLaren, Groppe et al. 2014](#)) ([Dimopolous, Hoang et al. 2018](#), [Fischer, Ochakovski et al. 2018](#), [Lam, Davis et al. 2019](#)).

Application of AAV2-REP1 to the retina requires retinal detachment following vitrectomy. The risks of vitrectomy and retinal detachment are summarized in [Section 5.4](#).

In line with guidance from regulatory agencies, the treatment intervals were chosen to comprehensively characterise the immunological profile following bilateral, sequential AAV2-REP1 treatment, and to reflect real-world application of gene therapy. As noted, both preclinical data with AAV2-REP1, and clinical data with sub-retinal administration of an AAV2 vector in subjects with Leber's congenital amaurosis, support bilateral administration of AAV2-REP1 in humans.

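### With an SE1-to-SE2 interval of 46 to 136 days, no first-eye visit is scheduled in the SAP's Month 12 window, so the supportive SE1 Month 12 row is selected by design in the short surgery window

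*SAP*

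**What the plan says.** Protocol 7.1 and SAP 3.3 end the first-eye schedule at SE2 surgery: "Post-treatment, subjects will no longer follow the Period 1 visit schedule, but will instead attend Period 2, Visits 2-9". SE1 is still examined, because "Ophthalmic assessments scheduled for Period 2, Visits 2-9 will be performed on both eyes", but on the timetable of the second eye. That timetable goes from Month 6 (±14 days) directly to Month 12 (±14 days).

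SAP 4.3 closes Period 1 on the day before SE2 surgery and gives SE1 a new baseline for Period 2. SAP 4.16.1 therefore adds a supportive BCVA analysis, for continuous and categorical endpoints. It reassigns Period 2 SE1 data to SE1 study day using Table 2 and takes change from the Period 1 baseline. The stated purpose is: "This way a full picture of Study Eye 1 treatment journey during the entire study will be presented". Table 2 sets Month 9 at Day 228-318, Month 12 at Day 319-410 and Month 15 at Day 411-501.

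The main BCVA analyses are observed case, with LOCF as supportive. SAP 4.17.1 puts the letter-loss categories in the same categorical tables as the letter-gain categories. SAP 4.7 lists surgery window (under 6, 6-12 and over 12 months, about 20 subjects each) as a BCVA subgroup. Protocol 10.1 asks investigators to time SE2 surgery to a planned Period 1 visit where they can.

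**The concern.** For a short-interval subject, the by-period tables cannot show SE1 at 12 months against its own pre-treatment value. Period 1 has ended by then, and the Period 2 SE1 baseline is itself a post-treatment value. The remapped table is the only planned table that can show it.

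If the schedule leaves the Month 12 window empty for a block of intermediate intervals, the short-window row at Month 12 consists mainly of subjects operated very soon after SE1 or close to 6 months after it. A reader who compares letter-loss proportions at Month 12 across surgery windows would compare a part of one group with nearly all of the others. Nothing in the SAP would warn that the cause is the schedule and not dropout. Loss of visual acuity is an identified risk (Protocol 5.4), and the interval between eyes is what the three windows exist to characterise, so this row is likely to be read.

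**Working it through.** **Inputs.** Target days and windows come from SAP Table 2; visit tolerances from Protocol 7.1. Let d be the SE1 study day of SE2 surgery. After surgery SE1 is scheduled on d+1, 3, 7, 14, 30, 91, 182 and 365.

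**1. Reproduce the Month 12 window.** The SAP's rule is that "the upper limit of the interval falls half way between the two visits". With target days 273, 365 and 456: (273+365)/2 = 319 and (365+456)/2 = 410.5. This gives Day 319-410, as printed.

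**2. Gap at target days.**
- The Period 2 Month 12 visit is in the window if d+365 ≤ 410, so d ≤ 45.
- The Period 2 Month 6 visit is in the window if d+182 ≥ 319, so d ≥ 137.
- For d = 46 to 136 the Period 2 Month 3 visit is too early (at most 136+91 = Day 227), and no Period 1 visit takes place after d.

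So d = 46 to 136 (91 values) has no scheduled assessment in the window. A check of every interval from 1 to 800 days shows no other gap at target days.

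**3. Gap with tolerances used in the most favourable direction.**
- Month 12 seen 14 days early: d+351 ≤ 410, so d ≤ 59.
- Month 6 seen 14 days late: d+196 ≥ 319, so d ≥ 123.

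An in-window scheduled visit is impossible for d = 60 to 122 (63 values). Conversely, it is planned but not assured for d = 32-45 and 137-150, because d+379 ≤ 410 needs d ≤ 31 and d+168 ≥ 319 needs d ≥ 151.

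**4. SE2 surgery at the Month 3 visit (Day 77-105).** The Period 2 Month 6 visit falls between 77+168 = Day 245 and 105+196 = Day 301. The Month 12 visit falls between 77+351 = Day 428 and 105+379 = Day 484. Both miss Day 319-410 whatever the tolerance.

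**5. Where the values go.** For d = 91, SE1 is seen on Days 92, 94, 98, 105, 121, 182, 273 and 456: a Month 9 value, then a Month 15 value. Across d = 46-136 the last two visits fall on Days 228-318 and 411-501. (Table 2 prints Month 6 as Day 137-272, which overlaps Month 9. The halfway rule gives an upper limit of Day 227. For d = 46-90 the d+182 visit lies in that overlap. This is a separate slip and does not alter the Month 12 gap.)

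**6. Share of the short group.** The interval distribution is not given. Assume an even spread from a start day to the end of 6 months:

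| Span | No value at target days | No value at best-case tolerance |
|---|---|---|
| Day 1-182 | 91/182 = 50% | 63/182 = 35% |
| Day 28-181 | 91/154 = 59% | 63/154 = 41% |

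Of about 20 subjects, this is roughly 10-12 and 7-8.

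**7. Medium window.** At target days nobody is lost. Within tolerance, d = 215-241 can miss: Month 3 seen early is before Day 319 if d+77 ≤ 318 (d ≤ 241), and Month 6 seen late is after Day 410 if d+196 ≥ 411 (d ≥ 215). At d = 228 these are Days 305 and 424.

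**8. Latest day of the next SE1 value.** Within the gap: 136+365 = Day 501 at target, and 136+379 = Day 515 at the limit of tolerance. For d = 150, an early Month 6 visit falls on Day 318, and the next visit can be as late as 150+379 = Day 529. At 365/12 days per month these are 16.5, 16.9 and 17.4 months.

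**The case against.** The strongest reply is that nothing confirmatory depends on this row. The remapping is supportive, the study is descriptive with no formal comparison, and SAP 4.16.1 does not say outright that the remapped tables will be cut by surgery window. All of that stands and limits the weight of the point.

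A reader might infer that these subjects lose their 12-month first-eye follow-up, contrary to Protocol 7.2: "A prospective trial period of at least 12 months following the administration of AAV2-REP1 in each eye is considered a sufficient period of time". The documents do not support that. The sentence concerns length of follow-up, and a completer in the gap has SE1 seen to about Day 411-501. Only the tabulation at Month 12 is affected.

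A reader might also infer that most of the short group is missing, or that the medium and long windows are complete. Neither is established. Protocol 9.8 and 10.1 provide for SE2 surgery before Day 21, so an even spread from Day 21 is not a given. Timing surgery to planned visits would cluster intervals: Day 14 and Month 1 targets lie outside the gap, Month 3 inside. Medium intervals of 215-241 days can also miss the window within tolerance. The six subjects whose SE1 was treated in an antecedent study have no Period 1 baseline, so they cannot enter the remapped table at all.

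Finally, other data could fill the row. LOCF, if it is meant to cover the remapped data (the SAP is unclear), would insert a value from before Day 319 under a Month 12 label. Unscheduled visits include BCVA and are assigned to windows, but they occur only when clinically indicated, so they would be selected values. Neither removes the selection.

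**Conclusion.** The gap is real and arises from the schedule. Absence of a scheduled Month 12 value holds for intervals of 46-136 days at target days, and is certain for 60-122 days whatever visit tolerance is used. It rests only on the Table 2 windows and the switch to the Period 2 schedule.

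The number of subjects affected is an assumption: 50-59% of the short group at target days, or 35-41% at best-case tolerance, if intervals are evenly spread to 6 months from a start between Day 1 and Day 28. The actual share could be smaller or larger.

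The consequence is limited. One row of a supportive table is selected for the short surgery window, and the sentence claiming completeness needs qualifying. It does not show that first-eye data are lost, that follow-up is too short, or that the main by-period BCVA analyses are wrong. It is worth correcting because no other planned table shows SE1 at about 12 months from its own baseline for short intervals.

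**What to change.** Leave the Table 2 rows as they are. In the remapped SE1 analysis add one supportive row, *first assessment at or after 12 months*. Define it as the first SE1 BCVA on or after Day 319, the opening day of the Month 12 window, with change from the Period 1 baseline. Set no upper cap, since a late Period 2 Month 12 visit can reach about Day 515, or Day 529 in the edge case shown above. Report the letter-loss and letter-gain categories for this row overall and by surgery window.

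Beside it, give the distribution of actual assessment days and the number of SE1 eyes with a Table 2 Month 12 value in each surgery window. Qualify the completeness sentence in SAP 4.16.1 by naming the gap. Exclude the subjects whose SE1 was treated in an antecedent study. Every Period 2 completer treated in both eyes within GEMINI then has an SE1 outcome at about 12 months or later.

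The cost is SAP wording and one derived row, with no added visit. The downside is unequal timing: some short-interval eyes contribute values from as late as about 16.5-17 months in a progressive disease. The row must therefore not be labelled Month 12 or replace the existing Month 12 row.
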